7.5 Follow-up of Adverse Events

All adverse events will be followed with appropriate medical management until resolved. Patients removed from study for unacceptable adverse events will be followed until resolution or stabilization of the adverse event. For selected adverse events for which administration of the treatment or procedure was stopped, a re-challenge of the subject with the investigational treatment or procedure may be conducted if considered both safe and ethical by the Investigator.

7.6 Adverse Events Monitoring

All adverse events, whether or not unexpected, and whether or not considered to be associated with the use of the study drug, will be entered into OnCore[®], as noted above.

The Investigator will assess all adverse events and determine reportability requirements to the UCSF Data and Safety Monitoring Committee (DSMC) and UCSF's Institutional Review Board, the Committee on Human Research (CHR); and, when the study is conducted under an Investigational New Drug Application (IND), to the Food and Drug Administration (FDA) if it meets the FDA reporting criteria.

All adverse events entered into OnCore[®] will be reviewed by the Helen Diller Family Comprehensive Cancer Center Site Committee on a weekly basis. The Site Committee will review and discuss at each weekly meeting the selected toxicity, the toxicity grade, and the attribution of relationship of the adverse event to the administration of the treatment or procedure.

In addition, all adverse events and suspected adverse reactions considered "serious," entered into OnCore[®] will be reviewed and monitored by the Data and Safety Monitoring Committee on an ongoing basis and discussed at DSMC meetings which take place every six (6) weeks.

7.7 Expedited Reporting

Within 24 hours of awareness of a serious adverse event, whether or not related to the study drug, the Investigator will complete and submit a Medwatch 3500A Form to FDA, containing all required information (reference 21 CFR 312.32). The Investigator will submit a copy of this MedWatch 3500A form to Astellas by either e-mail or fax, within the

same timeframe. If submission of this SAE to FDA, NCCN or Astellas is not possible within 24 hours, the Investigator's local drug safety contact (IRB, etc.) should be informed by phone.

The SAE documentation, including the Medwatch 3500A Form and available source records should be emailed or faxed to:

- Astellas Pharma Global Development – United States
- Email: [REDACTED]
- Fax number: [REDACTED]

In addition, email or fax to NCCN [REDACTED]. The following minimum information is required:

- Study number/IIT regulatory identifier
- Subject number, sex and age
- The date of report
- A description of the SAE (event, seriousness of the event)
- Causal relationship to the study drug

Follow-up information for the event should be sent promptly (within 7 days) as necessary.

Reporting to the Data and Safety Monitoring Committee

If a death occurs during the treatment phase of the study or within 30 days after the last administration of the treatment or procedure and it is determined to be related either to the treatment or procedure, the Investigator or his/her designee must notify the DSMC Chair (or qualified alternate) within 1 business day of knowledge of the event. The contact may be by phone or e-mail.

Reporting to UCSF Committee on Human Research (Institutional Review Board)

The Principal Investigator must report events meeting the UCSF CHR definition of "Unanticipated Problem" (UP) within 5 business days of his/her awareness of the event.

8 Tissue/Specimen Collection

8.1 Specimen Collection Summary for Translational Research

| Specimens Taken From Patient | Time of Collection |
|--|--|
| Diagnostic Core Biopsy Specimen(s) | 1) Pre-treatment 2) 4-6 wks after initiation of androgen deprivation therapy (at time of fiducial marker placement) 3) At the time of brachytherapy (if brachytherapy is being performed) |
| Whole blood: 50 mL of whole blood will be collected into green top tubes (sodium heparin). This should be collected, if possible, at the time of each blood draw for PSA and testosterone. | 1) Pre-Treatment 2) 4-6 wks after initiation of androgen deprivation therapy (at time of fiducial marker placement) 3) Within first 3 days of phase 2 brachytherapy 4) Month 3-4 post-radiation therapy |

Core biopsy specimens will be snap frozen in liquid nitrogen and stored at -80°C.

Plasma and whole blood samples will be processed and stored frozen at -80°C.

All samples will be de-identified and labeled with a case number. Samples will be sent frozen on dry ice via overnight carrier stored in a locked -80 °C freezer.

8.1.1 Plasma/Serum/Peripheral Blood Mononuclear Cell (PMBC) Banking

Immediately prior to each time point indicated above, the clinical research coordinator will assign unique specimen log numbers to be written on the specimen vials; this will ensure patient confidentiality. At the specified time points, 50 cc of whole blood will be collected in one green (sodium heparin) top tube that has been properly labeled with the unique specimen log number provided and stored at -80°C.

8.1.2 Tumor biopsy

Image guided biopsies will be performed prior to any treatment as part of the patient's diagnosis (may be performed up to 180 days prior to registration to confirm diagnosis of adenocarcinoma of the prostate; archival tissue will be collected if available), at 5 weeks post-initiation of enzalutamide therapy at the time of gold marker placement, and after 5 weeks of external beam radiation therapy at the time of brachytherapy (if patient decides to undergo brachytherapy). The biopsies will be performed by urologic surgical oncology and radiation oncology under transrectal ultrasound guidance with a 16-18 gauge needle. There will be minimal risk to these biopsies as similar or larger-gauge needles are already being inserted for fiducial marker placement (routinely used for daily setup for external beam radiation therapy) and HDR brachytherapy. Core biopsies will be extracted and will be immediately frozen on a pre-frozen bed of OCT (Optimal Cutting Temperature compound used for frozen sections), covered with additional OCT, and kept on dry ice or at -80°C.

All biopsies and blood samples will be delivered to the laboratory of [name] at UCSF, [REDACTED] or to the laboratory of [name] at UCSF, [REDACTED]. Both locations are secured, locked rooms with a locked liquid nitrogen storage tank and -80°C freezer. These samples will receive a patient-insensitive identifier and the link to patient identity will be kept in a locked file with access only by the principal investigators and the clinical research coordinator. Other co-investigators will have access to samples by submitting a request to the Committee on Human Research. Patients have the right at any time to request that all remaining samples be destroyed. Patients will be asked to consent to future, additional research on stored samples. Additional written consent will be required if additional samples are to be taken.

Deep whole exome sequencing of the tumor specimens with matched germ line samples (blood) will be performed on paired samples pre- and 5 weeks post-initiation enzalutamide treatment. The results will be compared across patients that do and do not obtain a biochemical complete response. Whole exome sequencing will allow for the identification of mutations, insertions/deletions, and copy number alterations involved in enzalutamide resistance. For exome sequencing, exons will be captured in solution from one microgram of sonicated genomic DNA using an Agilent SureSelect target capture system. Libraries of captured exons will be sequenced using 75 bp paired-end sequencing on an Illumina HiSeq with a goal of 100X coverage. Libraries will be constructed with indexing to allow sequencing of 3 or more exomes/lane. Computational analysis of raw exome data will be performed as described by our group. Somatic point mutations and indels nominated as clinically informative will be amplified and sequenced for validation.

Total RNA will be extracted, amplified, fragmented, and labeled. Gene expression profiling will be performed with the Affymetrix GeneChip Human Transcriptome Array 2.0. This microarray chip assesses the expression of over 1.4 million RNA features including ~22,000 known protein-coding genes as well as many thousands of non-coding RNAs. This will allow us to examine relative gene expression, splice variants, and immune response signatures.

9 Statistical Considerations and Evaluation of Results

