1.3 Rationale of the Proposed Study

Long-term androgen deprivation therapy consisting of a LHRH agonist, with or without the addition of an anti-androgen, with radiation therapy improves the survival of patients with high risk prostate cancer.^{1,2} Enzalutamide is a potent anti-androgen with at least 9- fold higher binding affinity than other anti-androgens such as bicalutamide. Thus, more profound androgen deprivation therapy with the addition of enzalutamide to LHRH agonist therapy may improve the clinical outcomes of patients. The primary objective is to assess the safety, tolerability, and feasibility of the addition of enzalutamide to LHRH agonist therapy in patients with very high-risk prostate cancer or pelvic node positive disease receiving radiation therapy. Also, the potential efficacy of enzalutamide and leuprolide in combination with radiation therapy for improving the PSA complete response will be assessed. We hypothesize that greater androgen blockade with addition of enzalutamide to LHRH agonist therapy will improve the PSA complete response and provide additional clinical benefit. The primary endpoint is to assess the impact of the addition of enzalutamide to LHRH agonist therapy in improving PSA complete response (PSA-CR) after radiation therapy. PSA-CR is defined as a PSA ≤ 0.3 ng/mL. This metric has been validated as a predictor of clinical outcome including disease-specific survival, distant metastasis, and biochemical failure in two large studies (RTOG 9413, n=1070; MSKCC, n=1045).^{9,10} In these studies, approximately 30% of patients failed to achieve a PSA-CR while on combined androgen blockade. Failure to obtain a PSA-CR was associated with significantly worse disease-specific survival, worse disease-free survival, higher incidence of distant metastases, and increased biochemical failure. Based on prior studies evaluating PSA response with enzalutamide, we would expect that addition of enzalutamide reduce the proportion of patients failing to achieve a PSA-CR to at least 0.15.

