2.4 Endpoints

2.4.1 Primary Endpoint

1. The primary endpoint of the study is to determine the rate of acute toxicity (≤ 90 days within the completion of radiotherapy) and late toxicity (≥ 91 days within the completion of radiotherapy). Adverse events will be defined according to CTCAE v. 4.0 criteria. Patients will be monitored at least weekly during treatment and every 3-6 months up to 24 months and at 36 months after radiation therapy.
2. A PSA measurement will be obtained at 120-127 days after initiation of androgen deprivation therapy. The proportion of patients achieving a PSA-CR (PSA nadir ≤ 0.3) at 120-127 days will be determined. The historical proportion of patients (0.7) attaining a PSA-CR from RTOG 9413 will be utilized for comparison.

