Normalization and summarization of data will be performed using the SCAN Algorithm. Genes with at least a 2-fold difference in expression will be selected. All statistical analysis will be performed using the MultiExperiment Viewer. Principal component analysis will be performed by eigenvalue decomposition of the 3 principal components for tridimensional classification of the samples and an unsupervised hierarchical cluster by Pearson's correlation will be selected to group the samples. The significance analysis of microarrays statistical technique will be performed for descriptive and comparative purposes. We will use the R package DESeq to perform differential gene expression analysis between response and nonresponse patients. We will use the R package GoSeq to perform over- and under-representation analysis (ORA) of gene sets taking length bias into account.

- Immune response signatures will be evaluated with the Affymetrix Gene Chip Array as described above. In addition, to examine the effect on T cell subsets, T cell turnover and T cell diversity, peripheral blood will be collected at pre-enzalutamide treatment, 5-weeks post-initiation of enzalutamide therapy at the time of fiducial marker placement, after 5 weeks of external radiotherapy, and at 4 months after completion of radiation therapy. T cell diversity will be performed using deep T Cell Receptor (TCR) sequencing and T cell turnover will be assessed by evaluating the number of TCR excision circles.

3 Study Design

*Leuprolide and enzalutamide for 24 months total.

*MRI– Multiparametric PET/MRI with DWI, DCE, Spectroscopy

#Biopsy will be performed at time of fiducial marker placement and at time of brachytherapy boost

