| Liver Function Tests including AST, ALT, and Total Bilirubin | X | X | X | X |
| Hepatitis B and C Testing | X | | | |
| Fasting Lipid Panel, glucose level, and HbA1c | X | | | X |
| 50 mL blood sample collection | Y | Y | Y | Y (month 3-4) |
| MRI prostate and pelvis | X | | | X (At time of PSA failure) |
| NaF PET/CT or Tc99m Bone Scan | X | | | X (At time of PSA failure) |
| EPIC-26, PROMIS, EQ-5D | X | | X (Before start of radiation therapy and after 5 weeks of conventional pelvic radiotherapy) | X |
| AE assessments | | X | Each week during external beam radiation therapy | X |

X = Assessments as determined by standard of care; Y = Additional procedure as part of study

^a Patients will be assessed at 6 weeks after completion of radiotherapy and then at least every 6 months thereafter for the first 2 years.

^b TRUS biopsies are optional and at provider discretion

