9.2 Determination of Sample Size and Accrual Rate

9.2.1 Sample Size and Power Estimate

Sample size is determined based on the primary objective of the PSA-CR. This is a single arm study with the primary endpoint evaluating the proportion of patients experiencing a PSA-CR. From historical controls (RTOG 9413 and MSKCC as mentioned in background information), we expect 70% of patients to experience a PSA-CR. With addition of enzalutamide, at least 85% of patients are expected to attain a PSA-CR. With 53 patients (10% dropout rate), we would have 80% power to detect thus improvement at significance level of 0.05 based on directional binomial test.

As we expect the combined enzalutamide and leuprolide regimen does not significantly increase grade 3 or greater acute or late toxicity for treatment of intermediate- to high-risk prostate cancer and the usual rate of 3 or greater toxicity is approximately 12%. If the true grade 3 or greater acute or late toxicity rate is 12%, with 47 patients we will have 80% confidence in the toxicity rate estimate with precision of 4.7% (i.e. a confidence interval width of 9.4%).

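### The resistance correlatives rest on a CR/non-CR split that leaves about 7–8 non-responders and ignores baseline PSA; a baseline-adjusted log-PSA analysis should be considered alongside it

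*Combined protocol and SAP*

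**What the plan says.** Section 8.1.2 plans exome sequencing of paired samples, taken before treatment and 5 weeks after enzalutamide starts, and then: "The results will be compared across patients that do and do not obtain a biochemical complete response". Section 2.4.3 plans to "perform differential gene expression analysis between response and nonresponse patients" but does not define response there.

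Section 1.3 gives the cut-off: "PSA-CR is defined as a PSA ≤ 0.3 ng/mL". It is an absolute level, whatever the starting value. Section 2.4.1 fixes the time: "A PSA measurement will be obtained at 120-127 days after initiation of androgen deprivation therapy". The response PSA is therefore recorded as a number before it is dichotomised. Baseline PSA is a screening item in section 6.1.1.

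For the expected split, section 9.2.1 says that "we expect 70% of patients to experience a PSA-CR" on the historical record and that with enzalutamide "at least 85% of patients are expected to attain a PSA-CR". On tissue, footnote b to Table 6 says "TRUS biopsies are optional and at provider discretion".

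Section 9.4.3 summarises PSA and models it over time, but does not link it to the genomic data. No correlative analysis uses PSA as a continuous variable or adjusts for its baseline value.

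**The concern.** The first two correlative objectives ask which alterations and expression patterns go with enzalutamide resistance. Answering that between patients needs a measure of response. A yes/no split with few patients on one side is a weak measure, and it weakens further the better the regimen works.

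The absolute cut-off adds a second difficulty. A patient who starts at a high PSA must have a larger proportional fall to be called a responder. A genomic feature that merely goes with a high starting PSA could then look like a resistance feature. Serial biopsies and sequencing would be spent on a contrast with little power and some exposure to confounding, although the two PSA values that would help with both are already in the database.

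**Working it through.** **Inputs from the documents.** CR rates of 0.70 and 0.85, 53 patients, 10% dropout, 80% power and one-sided 0.05 (9.2.1); 47 patients in the toxicity calculation (9.2.1); cut-off 0.3 (1.3). Baseline PSA can be below 20 through other risk features or nodal disease (3.2.1), and the PSA criterion is described as 20 to below 150 in section 3.1.

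**Plan's own figure.** The 15% non-CR rate comes from the sample-size calculation. With 53 × 0.9 = 47.7, rounded to 48, the normal approximation gives Φ[(0.15√48 − 1.645√(0.70 × 0.30)) / √(0.85 × 0.15)] = Φ[(1.039 − 0.754)/0.357] = Φ(0.80) = 78.8%, close to the stated 80%.

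**Non-responders.**
- 85% CR: 53 × 0.15 = 7.95 (95% binomial range 3–13); 47 × 0.15 = 7.05 (range 3–12, with a 15% chance of 4 or fewer).
- 70% CR: 53 × 0.30 = 15.9; 47 × 0.30 = 14.1.
- Missing biopsies can only lower these counts.

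**Information kept by the split.** For a normal outcome cut at proportion p, the asymptotic efficiency is φ(z_p)²/[p(1 − p)].
- p = 0.15: 0.2332²/0.1275 = 0.43, so 47 patients count as about 20.
- p = 0.30: 0.3477²/0.21 = 0.58, so 47 count as about 27.

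For values at the assay floor, a censored-normal model keeps 0.92, 0.82 and 0.65 of the information if 30%, 50% and 70% of patients are there. All three exceed 0.43.

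**Dependence on baseline.** Fall needed = 1 − 0.3/baseline: 94.0% from 5, 98.5% from 20, 99.7% from 100. Suppose the log10 fall has the same distribution in every patient (assumed SD 0.4–0.8), set so that 15% are non-CR at baseline 20. Then P(non-CR) = Φ[−1.036 + log10(baseline/20)/SD]. This is 1–4% at PSA 5 and 44–76% at PSA 100, with no difference in resistance.

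**False positives (simulation).** Assumptions: 47 patients, 15% non-CR, a feature whose carriers have log baseline PSA 0.8 SD higher, no resistance effect, two-sided 0.05. ρ is the correlation between log baseline and log day-120 PSA, which the documents do not give.

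| ρ | CR/non-CR split | log PSA, unadjusted | log PSA, adjusted |
|---|---|---|---|
| 0.3 | 8% | 12% | 5% |
| 0.5 | 12% | 23% | 5% |
| 0.7 | 19% | 38% | 5% |

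**Power (simulation).**
- Expression feature with an assumed correlation of 0.5 with log day-120 PSA and none with baseline, two-sided 0.001, 47–53 patients, no values at the floor, ρ from 0 to 0.5: adjusted log PSA about 62–91%, split at 85% CR about 11–17%. At 70% CR the split reaches about 23% with 47 patients.
- Mutation carried by 20% of 47 patients, assumed shift of one residual SD in log PSA, one test at 0.05, ρ from 0 to 0.7: Fisher's exact test on the split 44% falling to 27%, adjusted log PSA 71–75%.
- Weaker settings, 53 patients, unadjusted log PSA against the split: about 13% against 3% at a feature correlation of 0.3 (alpha 0.001); about 16% against less than 1% at a correlation of 0.5 with Bonferroni correction for 22,000 genes.

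**The case against.** **The split has a stated reason.** PSA-CR is the trial's efficacy endpoint. Section 1.3 describes it as validated against disease-specific survival and distant metastasis, and section 1.4 takes failure to reach it as a sign of resistant clones. A clinically anchored contrast is defensible in discovery work. This stands, and it is why the split should be kept. A reader might infer that log PSA ought to replace it; the documents do not support that.

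**Confounding is possible, not shown.** A reader might infer that burden-related genes will be reported as resistance genes. The documents give no correlation between baseline and day-120 PSA, or between any feature and baseline PSA. The table above rests on assumed values for both.

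**Continuous PSA alone is no remedy.** A reader might infer that moving to log PSA is enough. Without the baseline covariate its false-positive rate is higher than that of the split.

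**The loss depends on the CR rate.** Saying that most of the information is lost holds at 85% CR (43% kept) but not at 70% (58% kept).

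**Other analyses are planned.** Section 2.4.3 includes phylogenies and pre/post comparisons within patients, which differences in baseline PSA between patients do not affect. That is true, but they do not separate resistant from responding patients.

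**Adjustment has a price.** Section 1.4 lists AR amplification among the resistance mechanisms. If such alterations also raise baseline PSA, adjusting could remove real signal. Day-120 PSA also follows leuprolide and pelvic radiotherapy, so neither analysis isolates enzalutamide. Both points stand and favour reporting the two analyses together.

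**Section 2.4.3 does not define response.** Reading it as PSA-CR is an inference from section 8.1.2.

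**Conclusion.** The point holds as a suggestion to add an analysis. The only stated between-patient tests of resistance use a split with about 7–8 non-responders at the planned CR rate (14–16 at 70%). The split keeps roughly 43% of the information in a normal log PSA (58% at 70%) and takes no account of baseline PSA. The counts and the required falls follow from the plan's own figures; the efficiencies add the assumption that log PSA is normal.

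The power advantage, about 62–91% against 11–17%, rests on an assumed feature correlation of 0.5, alpha 0.001, a baseline correlation of 0 to 0.5 and no values at the assay floor. Both approaches lose power with weaker effects or transcriptome-wide correction. The direction of the baseline problem follows from the absolute cut-off; its size is unknown.

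Severity is consider. The objectives are exploratory, the primary conclusion and patient safety are untouched, and the PSA values are kept in any case.

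**What to change.** In sections 2.4.3 and 8.1.2:

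1. Keep the CR/non-CR comparison as the clinically anchored contrast, and state in 2.4.3 that response means PSA-CR at day 120–127, if that is intended.
2. Add a pre-specified analysis of log PSA at day 120–127 against each genomic feature, with log baseline PSA as a required covariate.
3. Name the method for undetectable values (censored or rank-based regression) and the multiplicity control.
4. Report both analyses side by side, with the number of patients in each group who had usable paired tissue.

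The cost is a few sentences and some extra exploratory analysis. No new samples, visits or measurements are needed. The drawback is that adjustment may remove signal from alterations that also raise baseline PSA; reporting both analyses lets a reader see where they differ.
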